7 DATA MANAGEMENT

7.1 Personal Data

Researcher captured anonymised data will be entered into a specially designed password protected online accessed secure database (RedCap). As detailed above, RedCap complies with stringent data security standards and is hosted within the University of Edinburgh Virtual Machine architecture which is physically secured. Participants will be identified on RedCap by study number alone. Patients who consent using the e-consent RedCap function will enter their name and signature into the system as part of the consent process.

Identifiable electronic information will be kept in a separate database, which will not be accessible outside the immediate research team. These data will be linked by study number to the anonymised research database and will be stored on a secure, password protected location on the local hospital (NHS Lothian) computer drive and only accessible to relevant staff.

Identifiable non-electronic data of the participant will be kept in a locked filing cabinet in a locked local research study office. Computers used to collate the data will have limited access measures via usernames and passwords. A fully anonymised version of the data will be shared on the Edinburgh University DataShare service and made available for 5 years after completion of the study.

Published results will not contain any personal data that could allow identification of individual participants.

[figure not shown]

Figure 3: Data flow diagram

Data stream	Data type	Where is database kept?	Who inputs data?	Who has access to data?	Is data anonymous?
HeadOn app www.headon-health.com	Email (mandatory) Name (optional) HeadOn ID Research ID Symptom type/severity Mood Sleep quality Alcohol consumption	Microsoft Azure cloud service	Study participant	Routine clinical care team (EMERGE research nurses) [name] (PI) [name] (MSc student) Pogo Studio Ltd (only if technical issue requiring support)	No. Email and name are identifiable. However, exported data is anonymised with HeadOn / Research ID and file is encrypted
RedCap database	Demographic Clinical examination Imaging findings Outcome data e-consent (name and signature)	Redcap is a medical database platform hosted by Edinburgh University	Routine clinical care team (EMERGE research nurses)	Routine clinical care team (EMERGE research nurses) [name] (PI) [name] (MSc student)	Yes, linked to identifiable patient data through research ID number
Study key (excel sheet)	Patient name, CHI; contact details; research number; recruitment data	Dataform containing patient name, CHI; contact details and research number which is kept on NHS Lothian computer network	Routine clinical care team (EMERGE research nurses)	Routine clinical care team (EMERGE research nurses) [name] (PI) [name] (MSc student)	No
Qualitative interview data	Audio recordings of qualitative interviews	Edinburgh university network	[name]	[name] (PI), [name] (MSc student)	Yes, only research ID used

Table 2: Data stream details

7.2 Transfer of Data

Data entry will be completed by the local research team and data analysis by the study statistician. Participants enter identifiable data (name/email address) outwith the local NHS region as part of the HeadOn registration process and RedCap e-consent function. Participant identifiable data will be removed from any electronic data being sent for analysis.

7.3 Data Controller

The University of Edinburgh and NHS Lothian are joint data controllers along with any other entities involved in delivering the study that may be a data controller in accordance with applicable laws.

The Chief Investigator will be responsible for the quality of the data recorded in the electronic CRF on the research database.

All Investigators and study site staff involved with this study will comply with the requirements of the Data Protection Act 2018 with regard to the collection, storage, processing and disclosure of personal information and will uphold the Act's core principles. Access to collated participant data will be restricted to those clinicians treating the participants, representatives of the sponsor and representatives of regulatory authorities.

7.4 Data Breaches

Any data breaches will be reported to the University of Edinburgh and NHS Lothian Data Protection Officers who will onward report to the relevant authority according to the appropriate timelines if required.

8 STATISTICS AND DATA ANALYSIS

8.1 SAMPLE SIZE CALCULATION

From admission data from the Royal Infirmary of Infirmary and St John's Hospital ED, approximately 1000 patients that meet our inclusion criteria present to the hospital every year. Over a 6-month period, there would be approximately 500 eligible patients. Assuming a recruitment rate of ~30% we are aiming to recruit 100 participant during the study period.

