1.2 RATIONALE FOR STUDY

Concussion is common and patients can go on to suffer with a constellation of symptoms which impacts their functional outcome and quality of life (McMahon *et al.*, 2013). Patient provision with information about their concussion and subsequent follow-up was highly variable in a prospective study in the USA (Seabury *et al.*, 2018). This is also the case with psychological therapies despite the fact there is evidence that CBT can help patients manage their symptoms after a concussion (Al Sayegh *et al.*, 2010).

We have developed HeadOn - a web application that delivers a CBT programme to patients following concussion. The application takes the patient through a 5-stage programme including: (i) understanding post-concussion symptoms; (ii) sleep after a concussion; (iii) lifestyle habits and exercise; (iv) managing negative thought patterns and (v) returning to baseline. The programme is delivered through a combination of weekly tasks (such as completing symptom diary, setting exercise goals and setting up a sleep time routine), audio/video media and reading material.

In this study, we would like to examine the feasibility of digitally delivering a course of CBT to patients following concussion. We hypothesise that patients will find it an acceptable and useful form of treatment. We plan on determining recruitment rates to guide future controlled trials.

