3 STUDY DESIGN

The HeadOn feasibility study is a prospective feasibility study of patients presenting to the Edinburgh Royal Infirmary and St John's Hospital Emergency Departments (ED) (**Figure 1**). Patients will be identified from the ED. Potentially eligible patients will be contacted by a member of the Emergency Medicine Research Group Edinburgh (EMERGE) research team and their consent will be sought for participation. Those not recruited at presentation to the ED will be contacted by telephone, text or email within two weeks of their concussion date to seek their participation in the study, again by a member of the EMERGE research team. After consenting, the participant will be taken through the registration process for the HeadOn program. For patients who are contacted after discharge they will be taken through registration process over the telephone or if preferable will be able to return to the ED to go over the process.

At registration the participant will be invited to complete a series of patient reported measures including the Rivermead post-concussion questionnaire, Pittsburgh Sleep Quality Index, PHQ9 questionnaire and FAST alcohol questionnaire within the HeadOn program. Alongside this, a series of researcher-led anonymised data points will be collected in a separate specially designed database including demographics, date of concussion, neurological and imaging findings which will all be collected from the medical notes and imaging reports. The HeadOn program runs for five weeks following which the participant will be invited to complete the same set of outcome measures. Alongside this, all the participant will be contacted (via telephone, text or email) by a member of the research team at week 5 to complete a further five measurements: Glasgow Outcome Score Extended, mHealth App Usability questionnaire, time to return to work and a healthcare utility questionnaire. Interested participants will be invited back within two months of enrolling in the study for a more detailed qualitative interviews about HeadOn. The study will recruit for a period of 6-months or up to 100 participants.

[figure not shown]

Figure 1: Schematic of HeadOn study design

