4 STUDY POPULATION

4.1 NUMBER OF PARTICIPANTS

The study aims to recruit over a 6-month period at the Royal Infirmary of Edinburgh and St John's Hospital ED with the aim to recruit 100 participants.

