4.3 EXCLUSION CRITERIA

- Patients aged under 16 years old
- Patients requiring surgical management of their cranial injury
- Significant other associated injuries requiring hospitalisation (spinal injury, fractures, abdominal, cardiothoracic or vascular injuries)
- Does not have capacity to give consent
- Non-English speakers
- Patient in police custody or in prison

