8.2.2 Recruitment rates

In this analysis, we will be calculating the recruitment rate as determined by the number of patients consenting to participate compared to those screened and eligible for recruitment.

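### Does the target of 100 participants in Section 8.1 contradict its own inputs, which give about 150?

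*Combined protocol and SAP*

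**What the plan says.** Section 8.1 starts from ED admission data: "approximately 1000 patients that meet our inclusion criteria present to the hospital every year". It halves that figure for a six-month period and then states: "there would be approximately 500 eligible patients. Assuming a recruitment rate of ~30% we are aiming to recruit 100 participant during the study period".

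Three other places bear on how to read the 100:

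- Section 3 sets the limits of recruitment: "The study will recruit for a period of 6-months or up to 100 participants".
- Section 4.1 gives the same duration and number as an intention: "The study aims to recruit over a 6-month period", "with the aim to recruit 100 participants".
- Section 8.2.2 defines the recruitment rate to be reported as "the number of patients consenting to participate compared to those screened and eligible for recruitment".

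The purpose of measuring recruitment is given in Section 1.2: "We plan on determining recruitment rates to guide future controlled trials". Section 8.1 contains no power, precision or attrition calculation. The primary endpoints in Section 2.2.1 are compliance and app usability, and Section 8.2.3 plans a descriptive analysis of compliance.

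**The concern.** Section 8.1 reads like a derivation: an annual number, a six-month number, a rate, then a target. A reader who multiplies through gets 150 at the last step and finds 100. The tilde on the 30% does not cover the difference. Since Section 8.1 is the only justification of study size, one would suspect that the rate, the pool or the target is wrong.

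Recruitment is also a stated objective and a secondary endpoint, meant to inform later trials. The ~30% is the only expected uptake in the document. If 100 of 500 eligible patients consented, the target would be met in full while uptake was 20%, one third below the assumption. Section 8.1 could then be cited to call recruitment either on plan or short of plan. A wrong input could also mislead anyone planning staffing or duration from this paragraph.

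**Working it through.** **Inputs, all from Section 8.1:** about 1000 patients a year, a six-month period, a recruitment rate of ~30%, and a target of 100.

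**Step 1, the plan's own intermediate figure.** 1000 × 6/12 = 500. This reproduces the stated number of eligible patients.

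**Step 2, expected recruits.** 500 × 0.30 = 150, against the stated 100. The difference is 50, a ratio of 150/100 = 1.5. Reading ~30% as 25% to 35% (an assumed range) gives 500 × 0.25 = 125 to 500 × 0.35 = 175. Neither end reaches 100.

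**Step 3, what would give exactly 100.**

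| Quantity changed | Calculation | Value needed | Stated in the plan? |
|---|---|---|---|
| Recruitment rate | 100/500 | 20% | No |
| Eligible patients in six months | 100/0.30 | about 333 | No |
| Further loss from 150 | 1 − 100/150 | one third | No |

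All three values are worked back from the target. None shows that a stated figure is wrong.

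**Step 4, the target as a limit.** Expected monthly accrual at 30% is 1000/12 × 0.30 = 25. With constant accrual from the first day (an assumption), 100 is reached at 100/25 = month 4. At 25% the pace is 20.8 a month and the date is 100/20.8 = month 4.8. At 35% the pace is 29.2 a month and the date is 100/29.2 = month 3.4. If two full months were lost at a rate of 30%, the date would be 2 + 4 = month 6. In each case 100 is reached within the window, so the inputs support 100 as attainable. The limit in Section 3 then closes recruitment.

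**Step 5, what depends on the choice.** The recruitment rate in Section 8.2.2 divides the number consenting by the number screened and eligible, both observed. The assumed 30% appears in neither. Closing at 100 before month 6 does not distort that rate, provided that the count of eligible patients stops when recruitment stops. The compliance groups and the usability questionnaire do not use the 30% either.

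For scale, the 95% half-width for a proportion of 0.5, such as the share fully compliant, is 1.96 × √(0.5 × 0.5/100) = 0.098 with 100 participants and 1.96 × √(0.5 × 0.5/150) = 0.080 with 150. Even recruiting the full 150 would gain only 1.8 percentage points.

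**The case for a change.** The strongest case for a change is that Section 8.1 is worded as a derivation and Section 4.1 calls 100 the aim over six months. No section says that 150 is expected, and one sentence would settle the matter. The 1000 are described as meeting the inclusion criteria, so exclusions such as "Significant other associated injuries requiring hospitalisation" may still have to come off. Yet the text calls the 500 eligible and states no reduction.

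Part of this stands. The document does not explain the step, and a reader cannot tell which account was intended. The ambiguity over whether 100 of 500 would count as on plan is also real.

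It does not carry further, for three reasons:

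- An aim that is below expected accrual is compatible with the inputs, and Section 3 supplies the limit that makes it coherent. That section allows recruitment to end at 100, so closing before six months is already provided for.
- The plan states no monthly pace. A pace of 100/6 = 16.7 a month arises only if the 100 must be spread over all six months, which Section 3 does not require.
- Incomplete screening is another possible account. Section 5.1 notes that these patients can leave the ED after a few hours, and Section 8.2.2 counts only those screened. If two thirds of the 500 were screened (an assumed figure), 500 × 2/3 × 0.30 = 100. Changing the rate or the pool to force agreement could therefore replace a correct input with a wrong one.

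As for later trials, they would draw on the observed rate and its denominator. The plan sets no success threshold at 30%, so no conclusion depends on that assumption.

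**Conclusion.** No change to the plan follows. The arithmetic behind the concern is right: the inputs give about 150, the target is 100, and no step connects them. This is an unexplained gap and not a demonstrated error. It amounts to 50 participants, with the target below expected accrual. The study would recruit up to the same limit, run the same analyses and report the same observed recruitment rate under any of the possible explanations.

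This rests on two readings: that recruitment in Section 3 ends at whichever limit comes first, and that the 30% is a planning assumption used nowhere else. The month 4 date also assumes constant accrual and that every eligible patient is approached. A sentence saying how the 100 was chosen would help a reader, but conduct, analysis and conclusions do not depend on it.

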8.2 PROPOSED ANALYSES

We plan on conducting the following analyses. The study PI will be performing the analysis:

8.2.1 Patient demographics

We plan on conducting descriptive analyses of patient demographics, clinical findings and imaging reports.

8.2.2 Recruitment rates

In this analysis, we will be calculating the recruitment rate as determined by the number of patients consenting to participate compared to those screened and eligible for recruitment.

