2.1.2 Secondary Objectives

Our secondary objectives are:

- Determining functional outcome after the HeadOn program
- Determining the temporal profile of post-concussion symptoms, sleep disturbance and mood during the study period
- Identifying return to work rates
- Recruitment rates of patients presenting to a single emergency department

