4.2 INCLUSION CRITERIA

- Patients aged 16 years and older (no upper age limit)
- Presenting to the ED with a concussion
- Concussion defined as a traumatically induced alteration of mental status (either defined as loss of consciousness and/or amnesia)
- Patient is Glasgow Coma Scale score of 13-15 on initial presentation to the ED
- Patient needs to be able to start using HeadOn within 14 days of their head injury

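### Section 8.2.2 does not say whether patients never reached count in the recruitment-rate denominator, so the rate may be overstated; separately, the recruitment figures in Section 8.1 do not agree with each other.

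*Combined protocol and SAP*

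**What the plan says.** Section 8.2.2 defines the recruitment rate as the number who consent "compared to those screened and eligible for recruitment". It does not say what makes a patient screened, or when eligibility is decided.

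Section 4.2 includes among the inclusion criteria: "Patient needs to be able to start using HeadOn within 14 days of their head injury".

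The matching secondary objective in Section 2.1.2 is worded by presentation: "Recruitment rates of patients presenting to a single emergency department". (Sections 3 and 4.1 name two EDs.) Section 1.2 says the rate is meant to inform later controlled trials.

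Section 8.1 works from admission data for both hospitals: "approximately 1000 patients that meet our inclusion criteria present to the hospital every year". It continues: "Over a 6-month period, there would be approximately 500 eligible patients". It then sets the target: "Assuming a recruitment rate of ~30% we are aiming to recruit 100 participant during the study period". Section 3 adds a stopping rule: "The study will recruit for a period of 6-months or up to 100 participants".

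Section 5.1 describes how patients are found: from triage information, clinical or electronic records, or ED admission logs. Those missed in the department are contacted within two weeks of the concussion.

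**The concern.** Whether a patient can start within 14 days is learned only by speaking to that patient. Sections 3 and 5.2 accordingly call patients only potentially eligible before they are approached. A patient who goes home after a few hours and is never reached can be logged as not confirmed eligible, and so leave the denominator. The same patient can equally be treated as screened and eligible on records, and stay in it. Both readings fit Section 8.2.2, and they give different rates from the same data.

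The choice matters because of the planned use. A later trial at these sites will start from ED attendances and will also lose patients before contact. A rate that leaves those losses out, applied to attendance figures, would forecast faster recruitment than the study showed.

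Section 8.1 should show which denominator was intended, but its own figures do not fit together.

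**Working it through.** **Inputs.** From Section 8.1: about 1000 patients a year meeting the inclusion criteria, a recruitment rate of about 30%, and a target of 100. From Section 3: recruitment for 6 months or up to 100 participants. The share u of record-eligible patients who drop out of the denominator, because they were not reached or not confirmed able to start by day 14, is not in the documents. It is taken here as an assumption from 0% to 50%.

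**Section 8.1 figures.**

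- Eligible patients in 6 months: 1000 × 6/12 = 500. This reproduces.
- Expected recruits: 0.30 × 500 = 150. The stated 100 does not reproduce.
- Rate that gives 100 from 500: 100/500 = 20%.
- Base that gives 100 at 30%: 100/0.30 = 333.
- Time to reach 100 at 30%: 1000/12 = 83.3 eligible patients a month; 0.30 × 83.3 = 25 recruits a month; 100/25 = 4.0 months.

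The figures are approximate in the text, but a gap between 150 and 100 is too large to be rounding.

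**Effect of the denominator.** Let C be the number consenting and E the number eligible on records. The record-based rate is C/E. If a share u of E leaves the denominator, the reported rate is C/(E(1−u)). The ratio of the two is 1/(1−u), whatever C and E are. With C = 100 and E = 500:

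| u (assumed) | Denominator | Reported rate | Factor 1/(1−u) |
|---|---|---|---|
| 0% | 500 | 20.0% | 1.00 |
| 10% | 450 | 22.2% | 1.11 |
| 20% | 400 | 25.0% | 1.25 |
| 33.3% | 333 | 30.0% | 1.50 |
| 40% | 300 | 33.3% | 1.67 |
| 50% | 250 | 40.0% | 2.00 |

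For scale, the 95% Wilson interval for 100/500 is 16.7% to 23.7%. At u = 20% the choice of denominator already moves the estimate beyond that interval.

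The 20% in the first row is not a benchmark. If recruitment stops at 100 after 4 months, E is 1000 × 4/12 = 333 and the record-based rate is 30%. The same factors then apply to 30%; at u = 20%, for example, 0.30/0.80 = 37.5%.

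**The case against.** The strongest reply is that the protocol never says unreached patients are excluded. Section 5.1 identifies patients from records and logs before any contact, so they can be regarded as already screened. A patient who was never reached has not been shown unable to start. This stands. A reader might infer that the planned rate does overstate recruitment, but the documents support only that it may.

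A reader might also infer that Section 8.1 uses a rate per ED attendance, in conflict with Section 8.2.2. It does not. Its base is presenting patients who meet the inclusion criteria, whom it calls eligible, so the two sections nominally share a base. Only the objective in Section 2.1.2 is worded by presentation. The narrower difficulty is that admission data would not show who could be reached or could start by day 14.

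Third, a rate among confirmed-eligible patients is a legitimate measure, and a record-based rate errs in the other direction. Capacity and English language (Section 4.3) may become clear only on contact, so the record-based denominator may include patients who are in fact ineligible. This also stands, and it is why both rates should be reported.

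Finally, it is tempting to correct Section 8.1 to 20%, or to quote a delay in months for a later trial. Neither follows. Section 3 lets 100 act as a cap, under which 30% is consistent, and any delay depends on an assumed u and an assumed trial size.

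The endpoint is secondary and descriptive, with no progression threshold. That limits the weight of the point, but the rate does have a stated planning use.

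**Conclusion.** Two points hold.

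First, the Section 8.2.2 denominator is undefined at the step that matters. Because the 14-day start is an eligibility criterion that records cannot settle, patients never reached may drop out. The reported rate would then exceed the rate among record-eligible presenting patients by 1/(1−u). The size cannot be obtained from the documents. It is nil at u = 0, a factor of 1.25 at an assumed 20% and a factor of 2 at an assumed 50%.

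Second, and without any assumption, Section 8.1 is internally inconsistent: its rate and base give 150, and its target is 100. Two readings reconcile the figures, a 20% rate over 6 months or a 30% rate with a cap reached at about 4 months. The text does not choose between them.

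**What to change.** In Section 8.2.2, define the steps and report a count at each, over the actual recruitment period (first to last recruitment day, which may be shorter than 6 months):

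1. identified from ED logs as meeting the criteria that can be checked from records;
2. contacted;
3. confirmed eligible and able to start by day 14;
4. consenting.

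Report consent over step 1, with unreached patients counted as not recruited, and also over step 3. State that the step 1 rate is the one to use for forecasts from ED attendance.

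In Section 8.1, restate the figures in one of two ways: a 20% rate is enough to recruit 100 of about 500 in 6 months; or 30% is expected and 100 is a cap, reached at about 4 months from about 333 eligible patients.

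The cost is wording and a flow table built from logs that staff already screen. Contact attempts must be logged prospectively, because they may not be recoverable later. The record-based rate will look less favourable and may include some patients who would have proved ineligible on contact; the report should say so.
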